2.2. Study Objectives

The primary objectives of this study are to describe the safety profile of c7vPnC within each study stage.

The secondary objectives of this study are to describe the immunogenicity of c7vPnC within each study stage.

CCI

3. INTERIM ANALYSES, FINAL ANALYSES, AND UNBLINDING

During this multistage study, the following analyses will occur:

Stage 1

1. Unblinded descriptive analyses of Stage 1 safety data through the visit occurring 1 month after vaccination to permit start of Stage 2.
2. Unblinded immunogenicity data from the visit occurring 1 month after vaccination from Stage 1 will be analyzed when data are available. Analyses will be descriptive.
3. Unblinded descriptive analyses of the safety data from the visit occurring 1 month after vaccination through the visit occurring 6 months after vaccination will be conducted when data are available.

Stage 2

1. Unblinded descriptive analyses for the visit occurring 1 month after vaccination for Stage 2 will be conducted when the safety and immunogenicity data are available.
2. Unblinded descriptive analyses of the safety data from the visit occurring 1 month after vaccination through 6 months and 12 months after vaccination will be conducted when data are available.

CCI

Investigator sites and laboratory personnel directly conducting the immunogenicity assays will remain blinded until the study database has been locked and unblinded.

4. HYPOTHESES AND DECISION RULES

4.1. Statistical Hypotheses

No formal statistical hypothesis testing will be performed. A descriptive estimation approach will be used to assess the safety and immunogenicity objectives in the study.

4.2. Statistical Decision Rules

Statistical decision rules will not be utilized in this study. All analyses are considered descriptive.

5. ANALYSIS SETS

Analysis sets for safety and immunogenicity data are defined in [Section 5.1](#) and [Section 5.2](#), respectively.

5.1. Safety Analysis Population

In Stage 1, the safety population will include all subjects who receive at least 1 dose of c7vPnC or Tdap. However, subjects who lack any safety data for an indicated analysis may be excluded from that analysis.

In Stage 2, the safety population will include all subjects who receive at least 1 dose of c7vPnC or PPSV23. However, subjects who lack any safety data for an indicated analysis may be excluded from that analysis.

Subjects will be assigned to vaccine groups corresponding to the vaccine actually received within each of the 2 study stages. The safety population will be the only analysis population for the primary endpoints for each study stage.

5.2. Other Analysis Sets

5.2.1. Immunogenicity Analysis Population

5.2.1.1. Evaluable Population

CCI evaluable populations are defined: the Month 1 evaluable population in each of Stage 1 and Stage 2 **CCI**. The evaluable population for each study stage will include any subject:

- who does not meet any exclusion criteria and meets all inclusion criteria,
- who has no major protocol deviations as determined by the clinician, and
- who receives the assigned vaccine, as randomized.

Additionally, for the Month 1 evaluable populations in Stage 1 and Stage 2,

- whose Visit 2 blood collection 1 month after vaccination is within 27 to 49 days, inclusive, after vaccination, and
- who has at least 1 valid and determinate assay result for at least 1 serotype for Visit 2.

The blood draw window has been expanded by 1 extra day before and 14 days after the protocol-specified blood draw window of 28 to 35 days, as has been established by precedent in the Prevnar 13 development program.

CCI

Individual samples may be excluded from statistical analysis plan (SAP)-specified immunogenicity analysis for reasons including, but not limited to, improper handling, insufficient volume, and inability to obtain a valid assay result; however, such a subject will still otherwise be included in the evaluable population, provided all other criteria are met.

The names for the evaluable populations will be “Stage 1 evaluable population,” “Stage 2 Month 1 evaluable population,” CCI

The evaluable populations will be the primary analysis populations for immunogenicity results.

5.2.1.2. All-Available Immunogenicity Population

All-available immunogenicity populations will be defined for each blood draw collection visit after vaccination. Each all-available population will include all subjects who receive vaccine and have at least 1 valid and determinate assay result at the indicated visit. The all-available immunogenicity populations will be the secondary analysis populations for immunogenicity results. Subjects will be assigned to their randomized vaccination.

The names for the all-available populations will be “Stage 1 all-available population,” “Stage 2 Month 1 all-available population,” CCI

5.3. Investigational Product Misallocations

All analyses will exclude data from subjects who are randomized but do not receive investigational product.

If a subject receives an investigational product that is not consistent with the investigational product to which he or she is randomized, for example, receives vaccine other than as randomized, then the subject will be reported under the investigational product that he or she actually received for all safety analyses, where applicable.

5.4. Protocol Deviations

A full list of protocol deviations will be compiled and reviewed to identify major and minor deviations prior to database lock.

5.4.1. Deviations Assessed Prior to Randomization

At screening in Stage 1 and prior to randomization in Stage 1 and Stage 2, the investigator will assess subjects against the inclusion and exclusion criteria as set out in Section 4.1 and Section 4.2 of the protocol.

5.4.2. Deviations Assessed After Randomization

Major deviations from the protocol will be reviewed for the protocol-specified unblinded analyses. Each major deviation will be evaluated regarding inclusion in safety or immunogenicity population before conducting the indicated unblinded analysis. The Stage 1 unblinded analyses will be performed on the safety data through 1 month after vaccination, the immunogenicity data from the visit occurring 1 month after vaccination, and the safety data through the visit occurring 6 months after vaccination (when the applicable data set is available). The Stage 2 unblinded analyses will be performed on the safety and immunogenicity data through 1 month after vaccination, the safety data through the visits occurring 6 months and 12 months after vaccination, **CCI**

Inclusion or exclusion of subjects from the indicated populations will not be changed for later unblinded analyses.

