5.3. Blinding of the Sponsor

In Stage 1, certain sponsor staff outside of the core study team will monitor unblinded safety data for events that trigger stopping rules or for unexpected safety findings as the data are collected. Sponsor core study team members will remain blinded to vaccine assigned/received at the subject level, following the principles outlined in ICH E9 guideline on Statistical Principles for Clinical Trials, Section 2.3.1,⁶⁰ until the analysis of all available safety data 1 month after vaccination. Study team members will review analyses in an unblinded manner.

In Stage 2, certain sponsor staff outside of the core study team will monitor unblinded safety data prior to the 1-month postvaccination analysis as the data are collected. Sponsor core study team members will remain blinded to vaccine assigned/received at the subject level until the analysis of all available safety and immunogenicity data 1 month after vaccination. Study team members will review analyses in an unblinded manner.

In both stages, sponsor personnel directly involved in evaluating subject data will be blinded to vaccine assignment as described above, following the principles outlined in ICH E9 guideline on Statistical Principles for Clinical Trials.⁶⁰ A data blinding plan will be created to describe the blinding requirements and unblinding events. The plan to control distribution of unblinded data among designated Pfizer personnel and core study team members will be specified in the data dissemination plan. Laboratory personnel performing the immunologic assays will be blinded until the study database has been locked and unblinded.

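### Judgment-based exclusions from the Stage 1 evaluable immunogenicity population may be decided after the core team's subject-level blind has ended

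*SAP*

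**What the plan says.** **When membership is decided.** SAP 5.4.2 states: "Each major deviation will be evaluated regarding inclusion in safety or immunogenicity population before conducting the indicated unblinded analysis". It then treats the Stage 1 analyses as distinct: "The Stage 1 unblinded analyses will be performed on the safety data through 1 month after vaccination, the immunogenicity data from the visit occurring" one month after vaccination, and later on the 6-month safety data, each when its data set is ready. The section closes by saying that membership of the indicated populations is not revised at later unblinded analyses. SAP 5.4 separately asks for the deviation review to be done before database lock.

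**When the blind ends.** Protocol 5.3 says for Stage 1: "Sponsor core study team members will remain blinded to vaccine assigned/received at the subject level", subject to ICH E9 principles, "until the analysis of all available safety data 1 month after vaccination". For Stage 2 the core team stays blinded "until the analysis of all available safety and immunogenicity data 1 month after vaccination".

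**Order of the analyses.** SAP 3 lists first "Unblinded descriptive analyses of Stage 1 safety data through the visit occurring 1 month after vaccination to permit start of Stage 2" and, as a separate item, "Unblinded immunogenicity data from the visit occurring 1 month after vaccination from Stage 1 will be analyzed when data are available". Protocol 9.5 matches.

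**What is judged.** Among the evaluable-population criteria in SAP 5.2.1.1, one reads "who has no major protocol deviations as determined by the clinician, and" and the next requires receipt of the randomized vaccine. The same section allows individual samples to be left out for reasons that are listed only as examples. The evaluable population is the primary one for immunogenicity.

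**The concern.** Analysis-set decisions that involve judgment should be made by people who do not know the vaccine group. In Stage 1 the written deadline for the immunogenicity decisions is tied to the immunogenicity analysis, while the blind is tied to the safety analysis. If safety comes first, there is an interval in which a deviation can be called major or minor, or a sample dropped, with the subject's vaccine known.

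What is at stake is the credibility of the first human OPA results for c7vPnC. With about 33 subjects per arm, a few exclusions handled more strictly in one arm than in the other can move a GMT or GMFR. A reader of the report could not tell from the plan whether the decisions were made blind.

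**Working it through.** **1. Order of events in Stage 1.**

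| Step | Source | Core team's subject-level blind |
|---|---|---|
| Visit 2 (1 month): data and blood collected | Protocol 6.1.3 | Intact |
| 1-month safety analysis, needed to start Stage 2 | SAP 3, protocol 5.3 | Ends here |
| 1-month immunogenicity analysis, when data are available | SAP 3 | Already ended, if this comes second |
| Deadline for immunogenicity deviation decisions | SAP 5.4.2 | Just before the immunogenicity analysis |

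The documents do not state that immunogenicity follows safety. They make it likely: the two are separate items, only safety gates Stage 2, and only immunogenicity has to wait for assay results.

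**2. Does another sentence close the gap?**

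- The closing sentence of SAP 5.4.2 prevents changes to a population already set. It does not say that the immunogenicity population is set at the safety analysis. The criterion of at least one valid assay result could not be applied then anyway.
- Review before database lock (SAP 5.4) does not help, because no lock is tied to the Stage 1 safety unblinding.
- SAP 3 and protocol 9.5 keep investigator sites and assay laboratory staff blinded. They do not mention whoever classifies deviations, and the clinician in SAP 5.2.1.1 is not defined.
- In Stage 2 the Month 1 blind ends only at the combined safety and immunogenicity analysis, so the gap is specific to Stage 1.

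**3. Which criteria are exposed?** The 27 to 49 day window, receipt of the randomized vaccine and a valid assay result are objective. The major-deviation judgment and the open-ended sample exclusions are not.

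**4. Size of the arm.** The plan randomizes about 66 subjects to obtain about 60 evaluable at 10% dropout (protocol 3.3). Adding 10% reproduces this: 60 × 1.10 = 66, or 33 per arm. Dividing by 0.90 gives 66.7, rounded up to 67.

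**5. Illustration of effect on a GMT.** Assume that k of n = 33 subjects in one arm are excluded, and that their titers are on average f-fold below the rest of that arm. The mean log titer with everyone included is lower than without them by (k/n) × log f, so

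GMT after exclusion / GMT before = f^(k/n).

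| Assumed f | k = 3 | k = 6 |
|---|---|---|
| 2 | 2^(3/33) = 1.065 (about 7%) | 2^(6/33) = 1.134 (about 13%) |
| 4 | 4^(3/33) = 1.134 (about 13%) | 4^(6/33) = 1.287 (about 29%) |

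The values of f and k are assumptions; the documents give neither.

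**6. Would the comparison population show it?** SAP 8.2.2 allows the all-available tables to be omitted when the evaluable population is at least 90% of all-available subjects. If all 66 are all-available, 6 exclusions leave 60/66 = 90.9% and 7 leave 59/66 = 89.4%. Up to 6 exclusions therefore permit the omission. The rule is not written per group, so all 6 could fall in one arm (6/33 = 18%).

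**The case against.** The strongest reply is that the gap may already be closed in practice. Deviations bearing on Month 1 immunogenicity have occurred by Visit 2, so they could be classified in the review held for the safety analysis. The closing sentence of SAP 5.4.2 could then be read as freezing membership from that point. Protocol 5.3 also promises a data blinding plan and a data dissemination plan, and the clinician may be a blinded site investigator. All of this is possible, but none of it is stated. The freeze sentence is ambiguous, and SAP 5.4.2 does not refer to the two plans, whose contents are not given. One sentence in the SAP would settle it.

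The reply is right on several limits:

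- Knowing the vaccine group does not reveal titers. Decisions are due before the immunogenicity analysis, so nothing in the plan gives a direct way to pick out low responders.
- Counts and reasons for exclusion must be tabulated (SAP 8.2.2), which leaves a visible trace even if the all-available tables are omitted.
- There are no hypotheses, decision rules or formal group comparisons, and Stage 2 starts on safety data.

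A reader might infer that the observer blind is compromised. The documents do not support that. Protocol 5.2 defines it through subjects and site staff other than the unblinded administrator, and sites and assay laboratory stay blinded until the database is locked and unblinded. Nor is the primary safety analysis exposed in the same way, since the safety population is defined by vaccine received (SAP 5.1).

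**Conclusion.** The point holds as a weakness in what the plan permits. For Stage 1 Month 1, the written deadline allows judgment-based exclusions from the primary immunogenicity population to be made after the core team may know each subject's vaccine. It rests on two readings: that the immunogenicity analysis follows the safety analysis, which is likely but not fixed, and that no unseen plan keeps the decision maker blinded.

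The consequence is moderate, because the affected endpoints are secondary and descriptive. The 7% to 29% range shows how sensitive an arm of 33 is under assumed 2-fold and 4-fold deficits, with 3 or 6 exclusions all in one arm. It should not be read as a forecast of bias, since the documents give no reason to expect that excluded subjects would be low responders or all in one arm.

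**What to change.** In SAP 5.4.2, add that:

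- all Stage 1 major deviations through Visit 2 will be classified by named roles blinded to vaccine group, and Stage 1 evaluable membership (apart from the valid-assay-result criterion) will be documented and fixed, before the 1-month Stage 1 safety unblinding;
- membership may change afterwards only through the valid-result criterion;
- any later exclusion of individual samples under SAP 5.2.1.1 will be decided by staff blinded to vaccine group.

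The blinded roles need naming because protocol 5.3 already has some sponsor staff outside the core team viewing unblinded safety data as they accrue. No separate lock of the safety population is needed.

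The cost is SAP wording and a deviation review held slightly earlier. The safety analysis already covers data through Visit 2, so the information for that review should be in hand, and no study procedure changes.

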6. ENDPOINTS AND COVARIATES

6.1. Safety Endpoints

The safety endpoints, which are primary endpoints of the study, include:

- Proportions of subjects reporting prompted local reactions within 14 days after vaccination (redness, swelling, and pain at the injection site), for each study stage.
- Proportions of subjects reporting prompted systemic events within 14 days after vaccination (fever, headache, fatigue, muscle pain, and joint pain), for each study stage.

- Proportions of subjects reporting AEs within 1 month after vaccination, for each study stage.
- Proportions of subjects reporting SAEs and NDCMCs within 6 months after vaccination (both Stage 1 and Stage 2) and within 12 months after vaccination (Stage 2 only).

6.1.1. Local Reactions

Within each study stage, the local reactions assessed and reported in the e-diary are redness, swelling, and pain at the injection site, from Day 1 to Day 14 following vaccination, where Day 1 is the day of vaccination.

Subjects will record presence or absence of redness and swelling. If present, the reaction will be measured and recorded in measuring device units (range: 1 to 21+). Measuring device units can be converted to centimeters according to the following scale: 1 measuring device unit = 0.5 cm. The reaction will be categorized for analysis as mild, moderate, or severe based on the grading scale in [Table 1](#) below. Redness or swelling less than 2.5 cm will be assigned as “none,” but such values will still be reported in the listings.

Pain at the vaccine injection site will be assessed by the subject as mild, moderate, or severe according to the grading scale in [Table 1](#).

Note that Grade 4 severities will not be collected in the e-diary but will be collected as AEs on the case report form (CRF). Grade 4 will not be analyzed as part of local reactions.

For each local reaction, the maximum severity grade of the reaction based on the severity grading scale of the local reactions in [Table 1](#) will be derived for the e-diary collection period (Day 1 to Day 14, where Day 1 is the day of vaccination) as follows:

= missing, if all values are missing for Day 1 to Day 14;

= 0 (or none), if the subject reports all reactions as “no” or a combination of missing and “no” for all Days 1 to 14 or (redness and swelling only) if the largest diameter is <5 measuring device units (ie, <2.5 cm);

= highest grade (maximum severity) within 14 days after vaccination (Day 1 to Day 14) among severity grades where the answer is not “no” for at least 1 day during Days 1 to 14.

Table 1. Grading Scales for Local Reactions

	Mild Grade 1	Moderate Grade 2	Severe Grade 3	Grade 4
Redness (erythema)	5 to 10 measuring device units = 2.5 to 5.0 cm	11 to 20 measuring device units = 5.5 to 10.0 cm	≥ 21 measuring device units = ≥ 10.5 cm	Necrosis or exfoliative dermatitis
Swelling (edema)	5 to 10 measuring device units = 2.5 to 5.0 cm	11 to 20 measuring device units = 5.5 to 10.0 cm	≥ 21 measuring device units = ≥ 10.5 cm	Necrosis
Pain at injection site	Does not interfere with activity	Interferes with activity	Prevents daily activity	Emergency room visit or hospitalization

Abbreviation: e-diary = electronic diary.

Note: If the size of the redness and/or swelling falls between 2 measuring device units, the higher measuring device unit number will be recorded in the e-diary.

Presence or Absence

For the data summary of the presence (yes or no) of a local reaction during Day 1 to Day 14 following vaccination, where Day 1 is the day of vaccination, the following variables are required:

- Maximum severity of each local reaction on any day (Day 1 to Day 14);
- Presence (yes or no) of each local reaction on each day (Day 1 to Day 14);
- Presence (yes or no) of each local reaction on any day (Day 1 to Day 14);
- Presence (yes or no) of any local reaction on each day (Day 1 to Day 14);
- Presence (yes or no) of any local reaction on any day (Day 1 to Day 14);
- Presence (yes or no) of each severe (Grade 3) (as defined in Table 1) local reaction on each day and any day (Day 1 to Day 14);
- Duration of each local reaction (duration will be calculated both from the first to the last day and also as total days with the indicated event);
- Onset day of each local reaction;

C [REDACTED].

For each local reaction, Table 2 below explains the algorithm to derive the presence of a reaction (yes or no) during Day 1 to Day 14 following vaccination, where Day 1 is the day of vaccination.

Table 2. Derived Variables for Each Local Reaction Within the Time Interval

Variable ^a	Yes (1)	No (0)	Missing (.)
Any Day 1 to 14	Subject reports the reaction as present (“yes”) on any Day 1 to 14. For redness and swelling this includes any nonzero measurement.	Subject reports the reaction as “no” on all 14 Days 1 to 14 or as a combination of “no” and missing on all 14 Days 1 to 14.	Reaction data are missing on all 14 Days 1 to 14.

- a. The variable will be derived for each of the local reactions (redness, swelling, pain at the injection site) and also for each of the severe local reactions within Day 1 to Day 14 following vaccination.

For any local reaction on any day, a similar rule applies as specified below in Table 3:

Table 3. Derived Variables for Any Local Reaction Within the Time Interval

Variable ^a	Yes (1)	No (0)	Missing (.)
Any Day 1 to 14	Subject reports “yes” or “mild” or greater for any local reaction on any Day 1 to 14.	Subject reports “no” on all 14 Days 1 to 14 or as a combination of “no” and missing on all 14 Days 1 to 14 on all 3 local reactions.	All 3 local reaction values are missing on all 14 Days 1 to 14.

- a. The variable will be derived for any local reaction (any redness, swelling, pain at the injection site) and also for any severe local reaction within Day 1 to Day 14 following vaccination.

Duration (From First Day to Last Day Reported)

The duration of each local reaction will be calculated as the number of days from the start of the first reported reaction to the resolution of the last reported reaction, inclusive. Days with redness or swelling with diameter <2.5 cm will be excluded. Resolution is the last day on which the reaction is recorded in the e-diary if the reaction lasted 14 days or less, or the date the reaction ended if it continued beyond Day 14 (the latter will be collected on the CRF). If there is no known date when the reaction ended, then duration will be missing (unknown). Subjects with no reported reaction have no duration because it is not applicable.

Duration of reactions ≥ 21 measuring device units will also be compiled.

Duration (Total Days Reported)

The duration (total days) of each local reaction will be calculated as the number of days with the reported reaction, including days after Day 14 (if any). Days with redness or swelling with diameter <2.5 cm will be excluded.

If there is no known date when the reaction ended, then duration (total days) will be missing (unknown). Subjects with no reported reaction have no duration because it is not applicable.

Total days of reactions ≥ 21 measuring device units will also be compiled.

Onset

The onset day of each local reaction and any local reaction will be derived. Days with redness or swelling with diameter < 2.5 cm will be excluded.

For the onset day of each local reaction, if subjects report severity change of the local reaction, only the first day of reporting that specific local reaction will be counted.

For the onset day of any local reaction, the first day of reporting any severity of any local reaction will be counted.

CCI

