7.2.2. Subject Electronic Diary

The subject will be asked to monitor and record local reactions, systemic events, fever, and antipyretic/pain medication used to treat symptoms, each evening for 14 days following vaccination (Day 1 through Day 14, where Day 1 is the day of vaccination) on a system that uses a personal digital assistant (PDA) or other technology. This system, hereafter referred to as the subject's e-diary, allows recording of these assessments only within a fixed time window, thus providing the accurate representation of the subject's experience at that time. Data on local reactions, systemic events, fever, and antipyretic/pain medication used to treat symptoms reported on the e-diary will be transferred electronically to the e-diary vendor, where they will be available for review by investigators, their appropriately qualified designees, and sponsor staff at all times via an internet-based portal. At intervals agreed to by the vendor and Pfizer, these data will be transferred electronically to Pfizer for analysis and reporting.

These data do not need to be reported by the investigator in the CRF. However, if a subject withdraws because of prompted events reported in the e-diary, the event(s) should be recorded on the AE page of the CRF, regardless of whether the investigator considers the event(s) to be clinically significant.

Investigators (or appropriately qualified designees) are required to review the e-diary data online at frequent intervals (daily is optimal) to evaluate subject compliance and as part of the ongoing safety review (see Stopping Rules in [Section 7.2.1](#)).

The investigator or designee must contact the subject in order to obtain stop dates for any reactions ongoing on the last day that the e-diary was completed. The stop dates should be entered in the CRF at Visit 2.

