6.1.2. Systemic Events and Fever

Within each study stage, the systemic events assessed and recorded in the e-diary are headache, fatigue, muscle pain, and joint pain, from Day 1 to Day 14 following vaccination, where Day 1 is the day of vaccination.

For each systemic event, the maximum severity grade of the event based on the severity grading scale in [Table 4](#) will be derived for the e-diary collection period (Day 1 to Day 14, where Day 1 is the day of vaccination) as follows:

- = missing, if all values are missing for Day 1 to Day 14;
- = 0, if the subject reports all reactions as “no” or a combination of missing and “no” for all Days 1 to 14;
- = highest grade (maximum severity) within 14 days of vaccination (Day 1 to Day 14) among severity grades where the answer is not “no” for at least 1 day during Days 1 to 14.

The symptoms of systemic events will be assessed by the subject as mild, moderate, or severe according to the severity grading scales of each systemic event in Table 4 below. Grade 4 will not be collected in the e-diary but will be collected as an AE on the CRF. Grade 4 will not be analyzed as part of systemic events.

Table 4. Grading Scales for Systemic Events

	Mild Grade 1	Moderate Grade 2	Severe Grade 3	Grade 4
Fatigue (tiredness)	Does not interfere with activity	Some interference with activity	Prevents daily routine activity	Emergency room visit or hospitalization
Headache	Does not interfere with activity	Some interference with activity	Prevents daily routine activity	Emergency room visit or hospitalization
Muscle pain	Does not interfere with activity	Some interference with activity	Prevents daily routine activity	Emergency room visit or hospitalization
Joint pain	Does not interfere with activity	Some interference with activity	Prevents daily routine activity	Emergency room visit or hospitalization

Abbreviation: e-diary = electronic diary.

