A listing will be provided for the subjects with severe (Grade 3) local reactions, systemic events, or fever >104°F (>40°C), or for any other unscheduled/unplanned safety assessment.

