8.2.1.3. Adverse Events

Descriptive summaries and listings of AEs will be provided. The descriptive statistics for AEs will be the number and percentage of subjects reporting at least 1 event of each preferred term with the associated Clopper-Pearson 95% CI ([Section 8.1.1](#)), arranged by system organ class. The number of occurrences of the event will also be compiled.

The AEs will be summarized for each vaccine group from vaccination until the visit for the blood collection 1 month after vaccination, for each of Stage 1 and Stage 2. In addition, tables with the same descriptive statistics for related AEs and AEs characterized as severe will also be compiled as described above.

SAEs and NDCMCs (defined in Section 8 of the protocol) will also be summarized for each vaccine group.

1. from vaccination until Visit 2 (1 month after vaccination) for each stage;
2. from vaccination until the 6-month follow-up for each stage;
3. from vaccination until the 12-month follow-up (Stage 2 only);
4. from Visit 2 (1 month after vaccination) until the 6-month follow-up for each stage;
5. from the 6-month follow-up until 12 months after vaccination (Stage 2 only).

The day of Visit 2 (1 month after vaccination) will be used to split the interval from vaccination to the 6-month follow-up. SAEs occurring on the day of the 1-month blood draw will be assigned to the interval “within 1 month after vaccination.”

AEs occurring immediately after vaccination, ie, within 30 minutes, will also be summarized for each stage.

AEs occurring after informed consent and before vaccination will be summarized for each stage.

Subjects in the safety population will be summarized according to the vaccine actually received.

CCI
[REDACTED]

[REDACTED]

[REDACTED]

[REDACTED]

[figure not shown]
[REDACTED]

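### Maximum-severity tables use the e-diary alone, so an investigator-confirmed Grade 4 prompted event can be shown there at a lower grade, as none or as missing, and no readable output labels it Grade 4 (minor)

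*SAP*

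**What the plan says.** The grading tables in both documents (Protocol Tables 1 and 2, SAP Tables 1 and 4) define four grades for redness, swelling, injection site pain, fatigue, headache, muscle pain and joint pain. Grades 1 to 3 come from the subject's e-diary. Grade 4 can be assigned only by the investigator and is recorded as an AE on the CRF (Protocol 7.2.3.1 and 7.2.3.2).

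SAP 6.1.1 derives maximum severity over the e-diary period, Days 1 to 14, and says that "Grade 4 will not be analyzed as part of local reactions". SAP 6.1.2 does the same for systemic events: "Grade 4 will not be analyzed as part of systemic events".

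Presence of a reaction has its own rule in SAP Table 2: "For redness and swelling this includes any nonzero measurement".

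For AEs, SAP 8.2.1.3 says "Descriptive summaries and listings of AEs will be provided", and that "tables with the same descriptive statistics for related AEs and AEs characterized as severe will also be compiled". SAP 8.2.1.1 adds: "A listing will be provided for the subjects with severe (Grade 3) local reactions, systemic events". That listing also covers fever above 104°F and extends further: "or for any other unscheduled/unplanned safety assessment".

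**The concern.** Prompted local reactions and systemic events are primary endpoints, and maximum severity is one of their main summaries. The derivation takes only diary entries, and the diary cannot hold the top grade. For an affected subject, the table therefore shows a lower grade than the investigator confirmed, or no grade at all.

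This would matter less if another output gave the number of Grade 4 events per group. The protocol footnotes to Tables 1 and 2, however, have the Grade 4 event graded again on the AE scale of Protocol 8.3, which ends at severe. The Grade 4 label is not carried into the AE tables. A reader who compares c7vPnC with Tdap or PPSV23 on the worst prompted reactions would not find that number in any output that can be read.

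**Working it through.** There is no stated figure to reproduce, because this is a derivation rule. The check has three parts.

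**1. Apply the SAP 6.1.1 and 6.1.2 rules to a subject with a confirmed Grade 4.** One measuring device unit is 0.5 cm. Redness is none below 5 units, mild at 5 to 10, moderate at 11 to 20 and severe at 21 or more.

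| Diary record, redness with confirmed necrosis | Maximum severity shown |
|---|---|
| No entry on any of the 14 days | Missing |
| Absent on some days, no entry on the rest | None |
| Largest entry 4 units (4 × 0.5 = 2.0 cm) | None |
| Largest entry 6 units (6 × 0.5 = 3.0 cm) | Grade 1 |
| Largest entry 15 units (7.5 cm) | Grade 2 |
| Largest entry 21 units or more | Grade 3 |

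No diary pattern gives Grade 4. The same holds for pain and the four systemic symptoms. For example, an emergency room visit for headache in a subject whose worst diary entry was moderate is shown as Grade 2. The rule affects 3 local + 4 systemic = 7 terms. Fever is graded by temperature range and has no Grade 4.

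Presence is less affected. In the last four rows Table 2 still counts the reaction as present. In the second row it is counted as absent. In the first row it is missing, and SAP 5.1 allows the subject to be left out of that analysis.

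**2. Follow the event through the other readable outputs.**

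- Preferred-term AE table and AE listings (SAP 8.2.1.3): the event is included. A prompted term on the AE page is not always Grade 4, however. Protocol 7.2.2 says "if a subject withdraws because of prompted events reported in the e-diary, the event(s) should be recorded on the AE page of the CRF", Protocol 7.2 sends acute reactions in the first 30 minutes there, and the AE table runs to Visit 2, beyond Day 14.
- Severe-AE table: included if the investigator rates the event severe on the three-level scale. It then stands with other severe AEs.
- SAE tables: included if serious. Protocol 8.2.4 notes that an emergency room visit is not necessarily a hospitalization.
- Listing in SAP 8.2.1.1: included if there is a Grade 3 diary entry, and possibly as an unscheduled assessment. It is not labelled Grade 4.

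**3. Size, as illustration only.** Assume that all 33 (Stage 1) or 220 (Stage 2) subjects planned per group are vaccinated and have diary data, that one has a Grade 4 event with a diary maximum below Grade 3, and that nobody else is severe. For the intervals use Clopper-Pearson, as in SAP 8.1.1. With no events the upper limit is 1 − 0.025^(1/n). With one event the lower limit is 1 − 0.975^(1/n), and the upper limit is the 0.975 quantile of a beta distribution with parameters 2 and n − 1.

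| Group | Planned severe row | Grade 4 line, if reported |
|---|---|---|
| Stage 1 | 0/33 (0 to 10.6%) | 1/33 = 3.0% (0.1 to 15.8%) |
| Stage 2 | 0/220 (0 to 1.7%) | 1/220 = 0.5% (0.01 to 2.5%) |

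If that subject's diary is empty and the subject is excluded, the planned rows become 0/32 (0 to 10.9%) and 0/219 (0 to 1.7%). If the diary already shows severe, the severe row includes the subject and only the Grade 4 label is missing.

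**The case against.** The best defence is that this is a disclosed design. Protocol and SAP agree that Grade 4 is kept out of the diary and collected as an AE. The endpoint concerns events that subjects report, so a table of diary data is faithful to it. AEs within 1 month are themselves a primary endpoint, tabulated by group with exact intervals, and severe AEs have their own table. Ordinary diary events need not be entered on the AE page, so prompted terms with onset in the first 14 days are there mostly because of Grade 4, withdrawal or an acute reaction. The listing covers unscheduled assessments and not only visits, so on a natural reading it also takes in a Grade 4 classified by telephone or from outside records. All of this stands, and it keeps the point minor. It does not supply a Grade 4 count, or tell the reader of the maximum-severity table that the top grade is reported elsewhere.

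A reader might infer several stronger things that the documents do not support:

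- That Grade 4 events drop out of safety reporting. They do not, as shown above.
- That the SAP contradicts the protocol. It follows the footnotes to Protocol Tables 1 and 2.
- That the proportions with any reaction are generally too low. They change only if no recorded diary day shows the reaction.
- That no Grade 4 output exists anywhere. Text is blacked out in SAP 6.1.1, 6.1.2, 8.2.1.1 and 8.2.1.3, and it may contain one.
- That stopping rules or the start of Stage 2 are compromised. The stopping rules are blacked out, and the Stage 2 start rests on Stage 1 safety data through 1 month, not on this table alone.

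**Conclusion.** The point holds as a minor reporting gap. By a stated rule, the maximum-severity tables can show a confirmed Grade 4 prompted event at Grade 3 or lower, as none or as missing, and no readable output identifies it as Grade 4. The effect is limited to the severity split in one set of tables. All analyses are descriptive, so no test or decision rule changes.

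The documents give no Grade 4 rate. The figure of one subject per group is an assumption, and the size depends both on Grade 4 occurring and on what the diary then shows. The conclusion about outputs rests on the readable text only. If a blacked-out part already provides a Grade 4 count, a pointer to it would be enough.

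**What to change.** Keep the e-diary tables as planned and make three changes to the SAP.

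1. In 8.2.1.1, beside the maximum-severity tables, report the number and percentage of subjects with an investigator-classified Grade 4 with onset on Days 1 to 14. Give this for each local reaction and for headache, fatigue, muscle pain and joint pain, by vaccine group and stage. Show each such subject's e-diary maximum, and include subjects with no diary data.
2. Name Grade 4 explicitly in the listing of severe events in 8.2.1.1.
3. Footnote the maximum-severity tables as e-diary only, with a pointer to the Grade 4 count and the AE tables.

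Cases can be identified from the AE records, checked against the immediate sponsor notification that Protocol 7.2.3.1 and 7.2.3.2 already require for every Grade 4. No CRF change is needed, nor a combined table of Grade 3 or above. The cost is a short count table, a few words in the listing, a footnote and a small review of AE records for seven terms. The one drawback is that the same event appears in two places, which the footnote makes plain.
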